### 2.7.3 Lab safety data

Trial stopping criteria included a decrease in fibrinogen to < 1.5gm/L at any time, and more than 50% decrease over 24hrs in the first couple of patients. No patient had <1.5gm/L during cohort 1, and notably, no reductions of fibrinogen as described above were seen during the treatment period and 48hrs after the last dose.

### 2.7.4 Exploratory biomarkers for fibrinolytic pathway

The plasma fibrinolytic pathway was evaluated through measurement of plasminogen, the precursor of plasmin and the alpha-2 antiplasmin its major inhibitor, and these were within normal limits.

Preliminary analysis of the tPA data show no changes were seen during tPA administration. Similarly, no changes in concentration of tPA antigen, PAI-1 antigen and tPA-PAI-1 complexes were seen. The abnormalities were consistent with COVID -19 with no evidence of any significant absorption of tPA or activation of the fibrinolytic pathway.

	baseline		day 3		day 5		day 13	
	Median	10% - 90%	Median	10% - 90%	Median	10% - 90%	Median	10% - 90%
No. of patients	9		9		8		2	
Plasminogen activity IU/dL	108	63.5 - 124.7	111	36.2 - 127.8	97.5	76.5 - 130	70 - 112	
Alpha 2 antiplasmin IU/dL	112.5	103.6 - 129 .4	116	104.6 - 128	119	106.1 - 139	112 - 116	
PAI -1 antigen ng/mL	41	31.6 - 58.4	39	28 - 54.2	38	26.8 - 92.2	25 - 35	
tPA antigen ng/mL	16.5	7.8 - 37.2	14	9 - 23	14	11.1 - 40	26 - 10	

In accordance with the MRC/DH/MHRA Joint Project Risk-adapted Approaches to the Management of Clinical Trials of Investigational Medicinal Products, this trial is categorised as:

- Type B = Somewhat higher than the risk of standard medical care

## 3 Objectives

### 3.1 Primary Objectives

1. Efficacy: Investigate the potential for efficacy of nebulised rtPA in patients presenting with severe COVID-19 requiring IMV or non invasive support with NIV OR continuous positive airway pressure (CPAP) OR high flow oxygen OR standard oxygen therapy
2. Safety: Evaluate the safety of nebulised rtPA treatment.

### 3.2 Secondary Objectives

1. Investigate the impact on patient's clinical status over time using the WHO ordinal scale of clinical improvement.

2. Investigate the effect of nebulised rtPA on other respiratory markers (such as lung compliance) and organ dysfunction
3. Investigate the impact on in hospital mortality and resource utilisation

### 3.3 Exploratory Objectives

1. Changes to coagulation and inflammatory markers concerning intervention and response to treatment.

## 4 Trial design

### 4.1 Overall design

This is a phase II, open label, single centre, uncontrolled, repeated dose, pilot trial of nebulised rtPA in patients with COVID-19 ARDS.

The study will recruit patients requiring either IMV or non-invasive oxygen support. Eligible patients (or if patients lack capacity, their legal representative) will be provided with an information sheet and informed consent will be sought (see section 6.3). Eligibility will be assessed via routine clinical assessments, which may have been done prior to consent. The only exceptions are a pregnancy test (blood or urine), and possibly any assessments listed in section 7.1 that were not done as per routine care. These must be done following consent, and all screening assessments must have been done during the 24-hour period before dosing with rtPA.

The study will run two cohorts sequentially. In cohort 1, 9 consented patients received nebulised rtPA in addition to SOC. 6 patients were receiving IMV and 3 were receiving non invasive support with NIV or CPAP or high flow oxygen or standard oxygen therapy. As an observational arm, matched historical controls who received standard of care were also recruited at a ratio of 2 controls to every 1 treatment arm patient, resulting in 18 historical controls. Originally, the study aimed to recruit 12 patients with 6 on each ventilation type (IMV and non-invasive oxygen support). This would have resulted in 24 historical controls. After the first wave of COVID-19 cases decreased in August 2020 in the UK it became difficult to continue recruitment, so recruitment closed for cohort 1.

With a second surge underway in early 2021, cohort 2 will aim to recruit more patients during this period to provide more data on the safety of rtPA. Based on the analysis of cohort 1, fewer timepoints will be collected (see sections 7.1.2 and 7.5.2), which will allow for more rapid recruitment while at the same time not compromising safety monitoring. A more flexible dosing regimen for rtPA will be utilised which is described in section 7.3.2. 30 patients will be recruited in total, with an aim to recruit a minimum of 10 IMV patients and 10 patients on non-invasive oxygen support.

A statistically powered randomised controlled trial (RCT) would be ideal to define the magnitude of benefit and impact on overall survival and is the typical design in patients with ARDS. Although there is clinical data on the safety of nebulised rtPA, but there is no clinical data in this clinical condition to facilitate a sample size calculation. There is data from a small RCT that has used another fibrinolytic agent, but the doses are not comparable(Abdelaal Ahmed Mahmoud et al. 2020). When a patient is randomised to receive no treatment, this precludes participation in other interventional studies which might decrease the risk of mortality. The most recent figures suggest a 50% mortality in patients receiving IMV there is 50% mortality. ([https://www.icnarc.org/About/Latest-News/2020/04/04/Report-Protocol-Version 10.0 dated 2 Feb 2021](https://www.icnarc.org/About/Latest-News/2020/04/04/Report-Protocol-Version-10.0-dated-2-Feb-2021))

On-2249-Patients-Critically-Ill-With-Covid-19) Currently there is a concerted effort to introduce multiple therapies based on our understanding of the pathophysiologic basis of disorder. Further, if this pilot study shows significant effect in a subset of patients, there would be justification to progress to a statistically powered RCT. We would progress to a RCT only after submission of a substantial amendment to this trial protocol or submission of a new clinical trial application. In the event of major adverse drug reactions or minor improvement in the oxygenation as assessed by  $\text{PaO}_2/\text{FiO}_2$ , there are minimal gains to be had with a larger randomised control study.

[figure not shown]
For patients in the rtPA group, 10 mg of rtPA dissolved in 5 ml of diluent will be given every 6 hrs for a maximum of 14 treatment days. Efficacy will be assessed by the monitoring of arterial oxygen saturation.

Safety monitoring will be performed by assessment of the incidence and severity of bleeding events, and by the monitoring of plasma fibrinogen levels and routine coagulation parameters. Additional samples will be taken for exploratory assessment of potential biomarkers, including (but not restricted to) PAI- 1, alpha 2 antiplasmin and a range of inflammatory cytokines and coagulation proteins. All other monitoring will be done as per SOC. From the end of the treatment phase both groups will be followed up in accordance with SOC.

Although there is extensive experience with the use of nebulised rtPA in the context of the underlying inflammation, safety measures been included. A gap of 24hrs will be maintained between first and second patient. At 24hrs if patient 1 has no evidence of major pulmonary bleeding suggesting exaggerated alveolar fibrinolysis and no evidence of fibrinogen reduction of more than 50%, suggestive of systemic absorption a second patient will be dosed. Both patients will be evaluated for 72 hrs. If no major bleeding is noticed and fibrinogen levels have not decreased more than 50% in either patient (in line with stopping criteria – section 7.10), and no other stopping criteria have been met, then the rest of the cohort can be recruited after the review of the safety data by the trial management group comprised of the investigators. If there are any concerns with the data this will be referred to the DMC for review. If the safety profile is acceptable, dosing of the third and subsequent patients in the rtPA group will resume with no required interval between patients.

Efficacy will be described as a change in  $\text{PaO}_2/\text{FiO}_2$  (or  $\text{SaO}_2/\text{FiO}_2$ ) ratio assessed daily, end of treatment and 5 days post treatment in relation to baseline. A Data Monitoring Committee (DMC) will be set-up to review safety data within the trial along with the final study results and advise on progressing from a pilot study to a randomised control trial based on the safety and efficacy data that is collected. The DMC will receive weekly reports on bleeding complications, both major and minor along with fibrinogen levels. If at any time a patient has major pulmonary bleeding, further dosing of patients will be stopped and an adhoc DMC review will be arranged before resuming dosing (see section 12.2 Data Monitoring Committee).

## 4.2 Schematic diagram(s) of overall trial design

## 5 Investigational Medicinal Products and Non-Investigational Medicinal Products

### 5.1 Name and description of IMP(s) - rtPA, alteplase (Actilyse®)

Actilyse 10 mg powder and solvent for solution for injection and infusion or Actilyse 20 mg powder and solvent for solution for injection and infusion.

1 vial with powder contains:

- 10 mg rtPA (alteplase) (corresponding to 5,800,000 IU) or
- 20 mg rtPA (alteplase) (corresponding to 11,600,000 IU)

Alteplase is produced by recombinant DNA technique using a Chinese hamster ovary cell-line.

The powder is presented as a colourless to pale yellow lyophilizate cake. The reconstituted preparation is a clear and colourless to pale yellow solution.

The reconstitution solvent is water for injections.

Actilyse is authorised as an intravenous formulation:

- Thrombolytic treatment in acute myocardial infarction
- Thrombolytic treatment in acute massive pulmonary embolism with haemodynamic instability
- Fibrinolytic treatment of acute ischaemic stroke

Actilyse is not authorised for administration via a nebulised route.

### 5.2 Source of IMP, Manufacture, Distribution and Storage

Actilyse will be supplied from existing hospital stock and replenished as required free-of-charge directly to the pharmacy by the manufacturer (Boehringer Ingelheim Ltd).

In this study Actilyse will be administered by nebulisation rather than intravenous injection. The rationale for selecting this route of administration is described in section 3.3.

A proof-of-concept nebulisation study (personal communication from [name], Boehringer Ingelheim) indicated that at the planned concentration of 2 mg/mL nebulisation produces a fine particle fraction of approximately 60%. This means that, in principle, 60% of the dose is able to reach the deep lungs.

The potential irritant effect of nebulised rtPA (with excipients: arginine, phosphoric acid for pH-adjustment, polysorbate 80) on the lungs is not known, but experience within the critical care setting indicates that risk will be low and manageable.

### **5.3 Storage and handling of IMP(s) at site**

All IMP aspects of the trial at participating sites are the responsibility of the PI, who may delegate this duty to the local pharmacist or other appropriately trained personnel. The delegation of duties must be recorded on the Staff Signature and Delegation of Tasks.

Storage must be in the original package in order to protect from light. Do not store above 25 °C. Actilyse will be reconstituted with water for injection in accordance with the instructions in the Summary of Drug Arrangements (SoDa) for the trial.

The reconstituted solution has been demonstrated to be stable for 24 hours at 2 °C – 8 °C and for 8 hours at 25 °C. From a microbiological perspective, the product should be used immediately after reconstitution. If not used immediately, in-use storage times and conditions prior to use are the responsibility of the user and would normally not be longer than 24 hours at 2 to 8°C.

For cohort 1, 10 mg of Actilyse reconstituted in 5ml of diluent provided will be used in an ultrasonic nebuliser available in the hospital. For cohort 2, 20mg will be reconstituted as directed in the SoDa, and will be used in an ultrasonic nebuliser available in the hospital.

Detailed instructions are contained in the summary of drug arrangements.

### **5.4 Accountability of IMP(s)**

IMP will be supplied by Boehringer Ingelheim Ltd to the hospital site. Details of initial supply and resupply will be detailed in the summary of drug arrangements.

The IMP Drug Accountability Log must be completed to record each dose of IMP dispensed for each trial participant. This log must be retained in the relevant section of the Pharmacy Site File, and a copy must be submitted to the sponsor upon request. It is the responsibility of the Pharmacy Lead to maintain drug accountability records.

All used/unused IMPs dispensed will be destroyed and not returned to pharmacy.

Detailed instructions are contained in the summary of drug arrangements.

### **5.5 Concomitant medication**

Concomitant medications will be recorded in the Participant's medical records/CRF.

No formal interaction studies with Actilyse and medicinal products commonly administered in patients with acute myocardial infarction have been performed.

Drugs affecting coagulation/platelet function

The risk of haemorrhage is increased if coumarine derivatives, oral anticoagulants, platelet aggregation inhibitors, unfractionated heparin or LMWH or active substances which interfere with coagulation are

administered (before, during or within the first 24 hours after treatment with Actilyse). This is particularly the case with intravenous administration; however, bleeding risk associated with nebulised administration, where absorption and systemic exposure is expected to be low, is not known.

There are now reports that standard prophylactic doses of anticoagulation have a high failure rate in COVID-19 pneumonia. As a result higher than standard doses are being used (including therapeutic anticoagulation) in these patients(Klok et al. 2020; Bikdelli et al. 2020) As the plasma concentration of rtPA is expected to be relatively low after nebulised administration, we do not expect concomitant administration of higher than standard doses of thromboprophylaxis to result in higher bleeding rates during this study. Use of anticoagulation at higher than standard doses is therefore not an exclusion criteria.

#### ACE inhibitors

Concomitant treatment with ACE inhibitors may enhance the risk of suffering a hypersensitivity reaction (see section 4.4).

Concomitant use of GPIIb/IIIa antagonists increases the risk of bleeding.

Where bronchoscopy is undertaken, diagnostic or therapeutic, it is reasonable to use topical tPA at a dose not exceeding 10 mg for the session.

## 5.6 Post-trial IMP arrangements

There will be no arrangements to provide IMP to patients after trial participation as patients would have either recovered or succumbed to their disease.

# 6 Selection of Participants

## 6.1 Eligibility of trial participants

### 6.1.1 Trial participant inclusion criteria – Cohort 1 and Cohort 2

All patients must meet the following criteria (ward or ICU based):

1. Patients with COVID-19 (confirmed by PCR or radiologically)
2.  $\geq 16$  years
3. Willing and able to provide written informed consent or where patient doesn't have capacity, consent obtained from a legal representative if available
4. Patients on mechanical ventilation must meet the following criteria:
  - a.  $\text{PaO}_2/\text{FiO}_2$  of  $\leq 300$
  - b. Intubated  $> 6$  hrs
5. Patients not intubated must meet the following criteria:
  - a.  $\text{PaO}_2/\text{FiO}_2 \leq 300$  or equivalent imputed by non-linear calculation from  $\text{SpO}_2/\text{FiO}_2$  (see look-up table in appendices)
  - b. In-patient  $> 6$  hours and being actively treated
  - c. On support with non-invasive ventilation OR continuous positive airway pressure (CPAP) OR high flow OR standard oxygen therapy

### 6.1.2 Trial participant exclusion criteria – Cohort 1

None of the following criteria must apply:

1. Females who are pregnant
2. Concurrent involvement in another experimental investigational medicinal product
3. Known allergies to the IMP or excipients of IMP
4. A pre-existing bleeding disorder (e.g. severe haemophilia) with no definitive treatment
5. Pre-existing severe cardiopulmonary disease (e.g. incurable lung cancer, severe chronic obstructive lung disease, cardiomyopathy, heart failure or impaired contractility <estimated 40% LVEF or RVEF)
6. Fibrinogen < 2.0 g/L at time of screening
7. Patients considered inappropriate for active treatment ( e.g. being considered for palliative care)
8. Patients with active bleeding in the preceding 7 days
9. Patients who in the opinion of the investigator are not suitable

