## 7 Trial procedures

### 7.1 Pre-treatment Assessments

#### 7.1.1 Screening – Cohorts 1 and 2

The results from the following routine procedures may be used to assess the participant's eligibility. Where routine results are not available at the time of consent, the procedure(s) will be carried out after consent. All must have been done within 24 hours prior undertaken as part of their standard care before their first dose of rtPA. These will also constitute the baseline assessments for cohort 2.

Patients receiving rtPA and SOC will undertake all assessments:

- Informed consent
- Demographics
- Review of medical history (including inpatient history and COVID-19 diagnosis – see section 7.7).
- Eligibility review
- Pregnancy test (blood or urine) for female participants of childbearing potential
- Concomitant medications
- Directed physical examination including vital signs (heart rate, temperature, blood pressure, and body weight)
- Documentation of respiratory status: Respiratory status of patients is monitored hourly and data points will be extracted for every four hour where available, but one data point is required as a minimum. The time of measurement should be documented. The variables include:
  - Details of oxygen and respiratory support including the type of device and FiO2  
Respiratory rate
  - PaO2
  - For IMV patients, details of ventilation including but not exclusively the below
    - Tidal volume (in mL)
    - Full sedation or not – not for cohort 2
    - Paralysis or not – not for cohort 2
    - Patient position – not for cohort 2
    - Peak inspiratory pressure (for computing compliance)
    - PEEP (for computing compliance )

- For non-invasive support patients:
  - SpO2
  - Oxygen flow rate
  - National Early Warning Score (NEWS 2) – not for cohort 2
- For CPAP patients
  - Positive end expiry pressure (PEEP)
- Local blood testing as per section 7.6.2
- Research blood sampling as per section 7.6.2
- Clinical status as assessed by 7-point ordinal scale (see section 7.7)
- Sequential Organ Failure Assessment (SOFA) score (see section 7.7)
- Glasgow coma scale (see section 7.7)

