### **10.4 Sample size and recruitment**

#### **10.4.1 Sample size calculation**

The sample size for this pilot study is not based on a statistical consideration. The recruitment target of 12 patients treated with rtPA and SOC is based on feasibility and the planned recruitment rate.

Similarly, for cohort 2 the sample size of 30 patients is not based on statistical consideration, but has been selected on the grounds of what is reasonable amid a second surge of COVID-19 admissions in early 2021 and the number of patients we might reasonably accept to recruit across the 2 sites over the next 2 to 6 weeks.

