b Local blood testing as per section 7.6.2 are to be done at a minimum once a day for cohort 1, or every other day for cohort 2, until 5 days after the last dose, and then as required until day 28, discharge or death whichever occurs first.

c Research blood sampling will be done once at baseline at 48 hours (+/- 24 hours), 96 hours (+/- 24 hours), and then twice weekly as per section 7.6.2. Twice weekly testing should be evenly spaced across weekdays if possible.

d Dosing schedule as per section 7.3

e End of study data will be collected at day 28, discharge or death whichever occurs first as per section 7.5.

f to be taken where available once daily for 3 days prior to dosing (cohort 1 only). Screening assessments can be used as part of this baseline period.

**21 Appendix 2 - Lookup table for imputed PaO2 for a given SpO2 based on non-linear equation (from Brown SM et al. Nonlinear Imputation of PaO2/FIO2 From SpO2/FIO2 Among Mechanically Ventilated Patients in the ICU: A Prospective, Observational Study. Crit Care Med. 2017; Aug;45(8):1317-1324)**

Measured SpO 2 (%)	Imputed PaO 2 (mmHg)
100*	167*§
99*	132*
98*	104*
97*	91*
96	82
95	76
94	71
93	67
92	64
91	61
90	59
89	57
88	55
87	53
86	51
85	50

Measured SpO 2 (%)	Imputed PaO 2 (mmHg)
84	49
83	47
82	46
81	45
80	44
79	43
78	42
77	42
76	41
75	40
74	39
73	39
72	38
71	37
70	37

\*Generally considered unreliable on the basis of the sigmoidal shape of the haemoglobin-oxygen dissociation curve

§Based on SpO2 99.5%.

Imputed values calculated using the following equation:

$$PO_2 = \left\{ \frac{\frac{11,700}{(1/S - 1)} + \left[ \frac{50^3}{11,700} \left( \frac{11,700}{1/S - 1} \right)^{1/3} + \left( \frac{11,700}{1/S - 1} \right)^2 \right]^{1/2}}{\left( \frac{11,700}{1/S - 1} \right)^{1/3}} \right\}^{1/3}$$

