## 22 Appendix 3 – Oxygen flow rate calculation (used for calculating FiO2 in patients receive non-invasive oxygen support)

Oxygen delivery devices		
Device	Flow rate	% Oxygen delivered (approx..)
Nasal Cannula	1 L/min	24%
	2 L/min	28%
	4 L/min	36%
Venturi Valve & Mask	Blue	2-4 L/min
	White	4-6 L/min
	Yellow	8-10 L/min
	Red	10-12 L/min
	Green	12-15 L/min
Non-rebreather Mask	15 L/min	85%

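### Criterion 5a allows entry on a P/F ratio imputed from SpO2 97–100%, rows that Appendix 2 flags as unreliable, and gives a measured PaO2 no precedence

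*Protocol*

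**What the plan says.** Section 6.1.1 of the protocol applies to both cohorts. Criterion 5 opens with "Patients not intubated must meet the following criteria". Its part (a) is PaO2/FiO2 of 300 or less, "or equivalent imputed by non-linear calculation from" SpO2/FiO2, with a pointer to the look-up table in the appendices. The synopsis repeats this. The SAP study summary repeats the imputation option without the pointer.

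Appendix 2 lists an imputed PaO2 for each SpO2 from 70% to 100%. The rows for 97, 98, 99 and 100% are starred, and the footnote to the star reads "Generally considered unreliable on the basis of the sigmoidal shape of the haemoglobin-oxygen dissociation curve". A second footnote says the 100% row is "Based on SpO 2 99.5"%. Appendix 3 converts oxygen devices to approximate FiO2, for example 36% for nasal cannula at 4 L/min and 85% for the entry "Non-rebreather Mask".

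Section 7.1.1 lists PaO2 among the screening respiratory variables for all patients, and SpO2 for those on non-invasive support. It takes readings where available, "but one data point is required as a minimum". It does not link that PaO2 to criterion 5a.

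**The concern.** Criterion 5a is the only test of oxygenation severity that a non-intubated patient must pass to enter a trial in ARDS. It joins the measured and imputed routes with a plain alternative. A site following it to the letter may use a starred row, even though the appendix warns against those rows. The warning sits in a table footnote and has no consequence in the eligibility text.

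At stake is whether the non-invasive group contains the intended patients. A well-oxygenated patient on a high oxygen setting can have a true ratio above 300 and still receive an imputed ratio below it. Such a patient would be given rtPA outside the target population and would blur the description of the group. Section 2.5 describes the oxygenation effect as apparently smaller in IMV patients, so the non-invasive group carries the more promising signal. Cohort 2 also has fewer bleeding-related exclusions than cohort 1 (section 6.1.4 against 6.1.2), so the severity criterion does more of the screening there.

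**Working it through.** **Inputs.** Threshold: P/F of 300 or less (section 6.1.1). Imputed PaO2 from Appendix 2: 167 mmHg at SpO2 100%, 132 at 99%, 104 at 98%, 91 at 97% (all starred), and 82 at 96% (highest unstarred row). FiO2 from Appendix 3: 0.24, 0.28 and 0.36 for nasal cannula at 1, 2 and 4 L/min, and 0.85 for a non-rebreather mask.

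**Reproducing the table.** The equation under Appendix 2 is garbled in the text available, so the standard inverse dissociation form with the same constants was used: a = 11,700/(1/S − 1), b = √(50³ + a²), PaO2 = ∛(b + a) − ∛(b − a). All 31 rows agree to the nearest mmHg. The top five are 166.7 (at S = 0.995), 131.9, 104.2, 90.6 and 81.9.

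**FiO2 at which each row meets the criterion.** Imputed P/F = imputed PaO2/FiO2, so a row passes once FiO2 is at least imputed PaO2/300:

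| SpO2 | Imputed PaO2 (mmHg) | Passes from FiO2 |
|---|---|---|
| 100%* | 167 | 167/300 = 0.557 |
| 99%* | 132 | 132/300 = 0.440 |
| 98%* | 104 | 104/300 = 0.347 |
| 97%* | 91 | 91/300 = 0.303 |
| 96% | 82 | 82/300 = 0.273 |

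**At FiO2 of about 0.56 or more.** The largest possible imputed ratio is 167/0.56 = 298, so every row passes. On a non-rebreather mask it is 167/0.85 = 196. A true ratio above 300 on that mask needs a PaO2 above 300 × 0.85 = 255 mmHg, which the table cannot return. On this route, at these settings, the criterion excludes nobody.

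**Below 0.557.** The starred rows still discriminate. At FiO2 0.36, SpO2 97% gives 91/0.36 = 253 (pass), 98% gives 104/0.36 = 289 (pass), 99% gives 132/0.36 = 367 (fail) and 100% gives 167/0.36 = 464 (fail). The decision therefore turns on one point of saturation within the range the appendix calls unreliable.

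**Dependence on the table.** The 0.557 figure comes from the table's cap. The uncapped equation gives 227 mmHg at SpO2 99.8% (passing from FiO2 0.76) and is undefined at 100%. The protocol directs sites to the table, so the cap is what applies.

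**The case against.** The strongest reply is that the imputed route may seldom be used. Criterion 5a names the measured ratio first. Section 7.1.1 lists PaO2 for every patient and says that results not routinely available are obtained after consent. Section 10.6.2 derives the primary endpoint from the PaO2 and FiO2 fields, so imputed values are not its stated source. The site sees the footnote when it uses the table, and the investigator may exclude anyone judged unsuitable. All of this stands and limits the reach of the point. None of it closes the gap: no text gives a measured value priority or bars the starred rows, and investigator discretion is not a defined severity test.

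A reader might infer that any patient on FiO2 of 0.56 or more is admitted whatever the true oxygenation, or that for starred readings the oxygen setting alone decides entry. The documents do not support either. The first holds only where the imputed value is the one relied on. The second fails below FiO2 0.557, as the 289 against 367 at FiO2 0.36 shows.

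It can also be said that readings near the cut-off cross it in the unstarred range too: at FiO2 0.24, SpO2 93% gives 67/0.24 = 279 and 95% gives 76/0.24 = 317. That is true, so crossing 300 is not itself the defect. The defect is reliance on rows flagged as unreliable, and a ceiling that leaves some settings with no failing value.

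Finally, limiting imputation to SpO2 of 96% or less means every permitted reading passes from FiO2 0.273 (82/0.28 = 293 at 2 L/min). This is not the same fault. It means only that an unstarred saturation at that FiO2 points to a ratio of 300 or less, using values the appendix does not disown.

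**Conclusion.** The point holds as a gap between criterion 5a and the protocol's own appendix. Following the stated rule can admit a non-intubated patient whose true ratio exceeds 300. On the imputed route this cannot be prevented from FiO2 0.557 upward. Below that, starred readings decide entry on values the protocol calls unreliable.

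The conclusion rests on two readings of the text: that sites use the table as printed, and that the two routes in 5a are equal alternatives. If sites always used a PaO2 when they had one, only patients without one would be exposed.

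The practical effect cannot be sized, because the documents do not say how many patients entered on imputed values or at what saturation. It would be wrong to infer that patients in cohort 1 were wrongly enrolled: nothing shows it, that cohort is closed, and it had only three non-invasive patients. Only cohort 2 can still change. Its analyses are descriptive and hypothesis generating (section 10.6), and of the sample size section 10.4.1 says "The sample size for this pilot study is not based on a statistical consideration", so no power or error-rate claim is affected. This is a worthwhile, inexpensive improvement and not a flaw that undermines the trial.

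**What to change.** Reconcile criterion 5a with the Appendix 2 footnote, in section 6.1.1 and the synopsis, and carry the same wording into the separate cohort 2 SAP:

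- A measured PaO2/FiO2 in the screening window takes precedence over an imputed value.
- Imputation is used only when no PaO2 is available, and only from the unstarred rows (SpO2 of 96% or less).
- At SpO2 of 97% or more, eligibility rests on the PaO2 already listed among the section 7.1.1 screening assessments.
- The rule applies to one pre-defined reading, for example the last before enrolment. Accepting any reading in the 24-hour window would invite choosing the lowest, which is undesirable when the endpoint is change from baseline.
- The eligibility form records whether the ratio was measured or imputed, and the SpO2 used.

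The cost is a short addition to the criterion and one or two form fields. No assessment is added to the screening list. The downside is that a few non-invasive patients without a PaO2 would be delayed or not enrolled.
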